**Study Cohort and Definition**

1. Concurrent vs. Neoadjuvant
  - a. Concurrent: ADT <= 30 days leading up or within 2 weeks after the RT start date.
  - b. Neoadjuvant: ADT >30 day leading up RT start date.
2. Toxicity Grade Scale  
Grade 1: Mild or pain does not interfere with activity

Grade 2: Moderate or repeated use of nonnarcotic pain reliever > 24 hours or interferes with activity

Grade 3: Severe or any use of narcotic pain reliever or prevents daily activity

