Information regarding disease characteristics (including stage, tumor size, grade), patient demographics (including age, race, co-morbidities, social history, body mass index), systemic treatment (including hormone therapy, systemic therapy), surgical treatment, radiation treatment, and clinical outcomes (local control, distant metastasis, survival, and treatment complications) will be collected and recorded.

Patients may also be asked to participate in a long term assessment between 1 and 10 years where they will complete the same study procedures as outlined above. Patients will be compensated \$50.00 for completing this visit.

A follow up phone survey will be taken between 18 months and 10 years after treatment. Using the same scales as in the study visits, the patients will be asked to rate their fatigue level, breast pain, how happy they are with the look of their breast and how different their radiated breast is from their non-radiated breast. They will also be asked if they are on any hormonal treatment for breast cancer and if so, the date they started. We will obtain verbal consent for this survey from patients who completed this study before the follow up phone survey was originally approved on 9/24/2013.

Assuming 10% of patients dropout, 53 patients requiring breast only radiation will be enrolled (2-3 patients per month) to yield a total of 50 patients.

An additional 33 patients requiring regional nodal irradiation and breast or chest wall radiation will be enrolled. Assuming 10% of patients dropout, 33 patients of these patients will be enrolled (2-3 patients per month) to yield a total of 30 patients receiving regional nodal irradiation and breast or chest wall radiation.

In patients undergoing regional nodal irradiation, arm measurements will be taken of the ipsilateral and contralateral upper extremity at baseline, 7 - 12 weeks, and 12 – 18 months post XRT by a licensed lymphedema therapist or study staff trained by a licensed lymphedema therapist. These patients will also be assessed for brachial plexopathy using RTOG grading toxicity, LENT/SOMA grading toxicity, and a modified version of a validated questionnaire to assess symptoms of brachial plexopathy at baseline and 7 - 12 weeks, and 12 – 18 months post XRT.[24] If a patient develops RTOG or LENT/SOMA Grade 3 toxicity, an objective measurement (MRI and/or nerve conduction studies) of brachial plexopathy will be employed.

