#### **Primary Outcome Measure:**

- Cutaneous Toxicity Rate Cutaneous toxicity rate will be assessed by the National Cancer Institute Common Toxicity Criteria (NCI-CTC) v 3. grading scale.
- 1. Rate of 20% or greater increase in arm lymphedema (compared to baseline arm measurements) will be assessed Among breast cancer patients receiving regional nodal irradiation
- 2. Rate of Grade 3 brachial plexopathy will be assessed among breast cancer patients receiving regional nodal irradiation by RTOG and LENT/SOMA scales

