**Data**

The SIB dataset was queried, and after exclusion and inclusion listed in the selection diagram file. Total 75 cases were included.

Selection and Exclusion Criteria	Sample Size	Excluded
SIB radiotherapy for breast cancer cases	75	-

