**Outcome and definition**

1. Skin Thickening Ratio (STRA) Baseline
2. Skin Thickening Ratio (STRA) at 1 year
3. Change in Skin Thickening Ratio (STRA) from Baseline to 1 year
4. Overall Survival was defined as months from the date of radiation ended to death or last seen at Emory.
5. Local Recurrence-free Survival (LRFS) was defined as months from the date of radiation ended to local recurrence or last seen at Emory.
6. Distant Recurrence-free Survival (DRFS) was defined as months from the date of radiation ended to distant recurrence or last seen at Emory.

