### **Statistical Analysis**

Statistical analysis was conducted using SAS Version 9.4, and SAS macros developed by Biostatistics and Bioinformatics Shared Resource at Winship Cancer Institute. Descriptive statistics for each variable were reported. Association between variables of interest and the study cohort were examined using ANOVA for categorical variables and Pearson correlation coefficient for continuous variables. Multi-linear regression between variables of interest and the study outcomes was examined. Variables were selected based on statistical significance on univariate analysis, while accounting for multicollinearity and removing variables with high rates of missing data.

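### The SAP's outcome list omits the protocol's primary toxicity outcomes, its 75 cases are not split into the two sized groups, and its only cohort is a loosely defined ADT split

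*SAP*

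**What the plan says.** **Protocol.** Under Primary Outcome Measure the protocol lists the cutaneous toxicity rate on the NCI-CTC v3 scale. It adds two outcomes for regional nodal patients: the rate of a 20% or greater increase in arm lymphedema, and a second worded "Rate of Grade 3 brachial plexopathy will be assessed among breast cancer patients receiving regional nodal irradiation by RTOG and LENT/SOMA scales". The section on patients requiring regional nodal irradiation sets hypotheses for these two (<15% and <3%) and lets the nodal group close while the other stays open. Data Collection sizes the groups separately: "53 patients requiring breast only radiation will be enrolled (2-3 patients per month) to yield a total of 50 patients", and for the nodal group 33 enrolled "to yield a total of 30 patients receiving regional nodal irradiation and breast or chest wall radiation". The same section schedules the nodal assessments: "In patients undergoing regional nodal irradiation, arm measurements will be taken of the ipsilateral and contralateral upper extremity at baseline" and at two later visits, with plexopathy assessed at the same times.

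**SAP.** Data says "Total 75 cases were included", in a single row. Outcome and definition lists STRA at baseline, STRA at 1 year, "Change in Skin Thickening Ratio (STRA) from Baseline to 1 year", overall survival, and local and distant recurrence-free survival. Study Cohort and Definition gives one contrast, concurrent against neoadjuvant. The concurrent level is "Concurrent: ADT <= 30 days leading up or within 2 weeks after the RT start date"; the neoadjuvant level is ADT more than 30 days before RT start. Statistical Analysis then states: "Association between variables of interest and the study cohort were examined using ANOVA for categorical variables and Pearson correlation coefficient for continuous variables".

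**The concern.** An SAP should say how the protocol's primary question will be answered. Followed as written, this one analyses skin thickening and survival. The toxicity rates on which the protocol rests its safety claim, and the two numerical limits for nodal patients, have no stated event definition, denominator or interval. A reader of the results could not tell from the SAP how many of the 75 patients were at risk of the nodal outcomes.

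The only grouping the SAP does define is one the protocol never mentions. It does not say what ADT is, which date the days are counted from, or where some patients belong. The association sentence then pairs categorical variables with that categorical cohort under ANOVA, which needs a continuous response.

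**Working it through.** **1. The two sets of outcomes side by side**

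| Protocol, Primary Outcome Measure | Population | Limit stated | In the SAP's outcome list? |
|---|---|---|---|
| Cutaneous toxicity rate, NCI-CTC v3 | All patients | 20% at Grade 3 (Monitoring Plan) | No |
| 20% or greater increase in arm lymphedema | Regional nodal | <15% | No |
| Grade 3 brachial plexopathy | Regional nodal | <3% | No |

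The SAP does print a three-level toxicity scale, but it is worded around pain, analgesic use and activity and is tied to no listed outcome. The supplied SAP text nowhere mentions nodal irradiation, lymphedema or plexopathy.

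**2. The group sizes**

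Planned yields are 50 + 30 = 80, which matches the eighty patients in Study Design. The nodal enrolment reproduces: 30 × 1.10 = 33 (30/0.90 gives 34). The SAP's 75 cannot be divided from the documents. Pro rata to the plan it would hold 75 × 30/80 ≈ 28 nodal patients; this is an assumption.

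**3. The ADT rule, read as the day ADT started relative to RT start**

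| Start of ADT | Level |
|---|---|
| Before day −30 | Neoadjuvant |
| Day −30 to day +14 | Concurrent |
| Day +15 or later | None |
| Never | None |

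There is no gap at the 30-day boundary. If any exposure counts instead of the start date, a patient treated from before day −30 through RT start meets both definitions. How many of the 75 are affected is unknown.

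**4. The association sentence**

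With a categorical variable and a two-level cohort, both sides are categorical, so the natural analysis is chi-square or Fisher exact. ANOVA fits if the response is STRA and the categorical variable is the factor, but the sentence names the cohort, not STRA.

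**5. What the nodal group can show**

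For 0 events in n, the exact two-sided 95% upper limit is 1 − 0.025^(1/n).

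| Nodal n (assumed) | Upper limit, 0 events |
|---|---|
| 25 | 13.7% |
| 28 | 12.3% |
| 30 | 11.6% |
| 33 | 10.6% |

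Plexopathy: one event is 1/30 = 3.3%, and even 1/33 = 3.03%. With 33 or fewer nodal patients, the observed rate is below 3% only with no events, and even then the interval does not exclude 3%.

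Lymphedema, with 30 nodal patients: 4/30 = 13.3% (exact 95% CI 3.8% to 30.7%) is below 15%; 5/30 = 16.7% (5.6% to 34.7%) is above it. An interval wholly below 15% needs 0 events (upper limit 11.6%); with 1 event the upper limit is 17.2%.

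**6. Skin toxicity, overall and by group**

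The Monitoring Plan's 16 of 80 is 20%. At an observed 20%, the exact 95% CI is 11.7% to 30.8% for 15/75, 10.0% to 33.7% for 10/50 and 7.7% to 38.6% for 6/30.

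**The case against.** **The SAP may cover more than it lists.** Its variables of interest are not enumerated, descriptive statistics are promised for each variable, a selection diagram file is cited but was not supplied, and an SAP passage was removed before review. Rates are descriptive statistics, so the nodal outcomes could have been tabulated. This limits the claim to what the supplied text specifies. It does not fill the gap: no event, denominator or interval is named, and nodal irradiation as a covariate in an STRA regression would not produce a lymphedema or plexopathy rate.

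**Pooling is partly the protocol's own design.** Study Design recruits eighty patients and the Monitoring Plan sets the skin limit at 16 of 80. This stands. A combined skin-toxicity rate is legitimate and should be reported. The separate sizing and the separate stopping tables (to 50 and to 30 patients) support a rate within each group as well.

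**The ADT rule is usable.** On a start-date reading it classifies every start up to day +14, and the contrast may be meant for treated patients only. This also stands, so it would be too strong to say that the rule cannot be applied. The undefined term, the unstated clock and the unstated coverage remain.

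**A tempting stronger reading** is that nodal events will be divided by 75 and so appear to fall under the limits. The documents do not support it. The SAP proposes no such denominator, and the protocol ties both rates, and the scheduled arm and plexopathy assessments, to nodal patients. The defect is silence, not dilution.

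**The small nodal group limits what the fix can decide.** That is true and should be reported; it is no reason to leave the outcomes out.

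**Conclusion.** The point holds as a gap in coverage and definition. None of the three toxicity outcomes under the protocol's primary heading appears in the SAP's outcome list, and the two nodal limits have no written analysis. The 75 cases are not split into the groups the protocol sized. The sole cohort rests on a term absent from the protocol, with at least two kinds of patient unplaced on a start-date reading, and the ANOVA pairing is not valid as worded.

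No bias in a reported rate is shown, and the number of patients outside the ADT levels is unknown. The precision figures assume a nodal group of about 30. Over 25 to 33, the upper limit for zero plexopathies runs from 13.7% to 10.6%, so the conclusion that 3% cannot be excluded does not depend on that choice. The absence of an expansion for ADT is judged on the supplied text only.

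**What to change.** - Add the three primary toxicity outcomes to the SAP, with event definitions and assessment times taken from the protocol.
- State how many of the 75 are breast-only and how many are nodal.
- Report lymphedema and Grade 3 plexopathy on the nodal denominator. Report Grade 3 skin toxicity both overall, to match the Monitoring Plan, and within each group. Give each an exact 95% CI; no between-group test is needed.
- Remove the ADT split. Otherwise define ADT and the date from which days are counted, state whom the split covers, and label it exploratory.
- Name STRA as the response for ANOVA and Pearson, and use chi-square or Fisher exact for categorical-by-cohort tables.

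The cost is SAP wording and re-run tables. The protocol already provides for recording radiation treatment, arm measurements and plexopathy assessments, so no new data are needed. The downside is wide intervals in the smaller groups. The report should say plainly that, with about 30 nodal patients, a plexopathy rate of 3% cannot be excluded even if no event is seen.

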### **Statistical Analysis**

Statistical analysis was conducted using SAS Version 9.4, and SAS macros developed by Biostatistics and Bioinformatics Shared Resource at Winship Cancer Institute. Descriptive statistics for each variable were reported. Association between variables of interest and the study cohort were examined using ANOVA for categorical variables and Pearson correlation coefficient for continuous variables. Multi-linear regression between variables of interest and the study outcomes was examined. Variables were selected based on statistical significance on univariate analysis, while accounting for multicollinearity and removing variables with high rates of missing data.

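### The SAP aims its univariate ANOVA and Pearson tests at the study cohort although they fit the STRA outcomes, so read literally covariates are screened on the wrong target

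*SAP*

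**What the plan says.** The SAP's Statistical Analysis section describes one univariate association analysis: "Association between variables of interest and the study cohort were examined using ANOVA for categorical variables and Pearson correlation coefficient for continuous variables". It continues: "Multi-linear regression between variables of interest and the study outcomes was examined". Variables for that regression are chosen by significance on univariate analysis, after allowing for multicollinearity and dropping variables with much missing data. The section does not say which univariate analysis is meant and gives no significance threshold.

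The SAP's Study Cohort and Definition section has two items. The first is "Concurrent vs. Neoadjuvant", split as "Concurrent: ADT <= 30 days leading up or within 2 weeks after the RT start date" and "Neoadjuvant: ADT >30 day leading up RT start date". The second is "Toxicity Grade Scale", with grades 1 to 3.

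The Outcome and definition section lists six outcomes. Three are STRA measures (baseline, 1 year, and "Change in Skin Thickening Ratio (STRA) from Baseline to 1 year"). The other three are times from the end of radiation to an event or last contact, for example "Overall Survival was defined as months from the date of radiation ended to death or last seen at Emory"; local and distant recurrence-free survival have the same form. The Data section gives 75 cases.

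**The concern.** The tests named do not match the target named. Nothing under the cohort heading is a continuous measurement, so a reader expects chi-square or Fisher's exact test for categorical variables and a t-test or rank test for continuous ones. The tests that appear are those for a continuous outcome, and the SAP's continuous outcomes are the STRA measures.

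The consequence reaches the regression. If the cohort screen decides which variables enter a model for STRA, a variable that predicts STRA but is balanced between cohorts will usually be dropped, and a variable that differs between cohorts but has no bearing on STRA may be kept. A reader cannot tell from the SAP which screen was used, so the selected models cannot be reproduced from the plan.

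**Working it through.** The section states no sample size, power or alpha that could be reproduced. The check therefore sets the sections side by side and then sizes the effect at the SAP's 75 cases. Two-sided 0.05, the correlations, the cohort shares and the example table are assumptions; the documents give none of them.

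**1. Test against target**

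| Possible target | Type | Do ANOVA and Pearson fit? |
|---|---|---|
| Concurrent or neoadjuvant | two groups | not the standard choice; see steps 3 and 4 |
| Toxicity grade | three ordered levels | not the standard choice |
| STRA: baseline, 1 year, change | continuous | yes |
| Overall, local and distant recurrence-free survival | censored time | no |

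The named pair fits only the STRA row. In simulation at n = 75, ANOVA of a continuous outcome over a two- or three-level covariate had a type I error of 0.048 in both cases.

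**2. Cost of screening on the wrong target**

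Take a covariate with correlation r to the outcome. The probability that it passes a two-sided 0.05 screen on the outcome is about Φ(atanh(r)·√(n − 3) − 1.96), with √72 = 8.485.

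- r = 0.3: 0.3095 × 8.485 = 2.626; Φ(0.666) = 0.75
- r = 0.4: 0.4236 × 8.485 = 3.595; Φ(1.635) = 0.95
- r = 0.5: 0.5493 × 8.485 = 4.661; Φ(2.701) = 0.997

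Simulation gave 0.755, 0.952 and 0.997. When the same covariate was screened on a two-group cohort unrelated to it (equal split assumed), it was kept in 0.053, 0.051 and 0.051 of runs. That is the false-positive rate of the screen and does not depend on r.

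**3. Continuous variable against a two-group cohort**

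Pearson correlation with a 0/1 cohort is algebraically the pooled t-test. In three simulated data sets of 75, with 15, 25 and 37 in one group, Pearson, t-test and one-way ANOVA gave identical p-values: 0.0188, 0.1038 and 0.0206.

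**4. Categorical variable against a two-group cohort**

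There are two ways to run an ANOVA here, and the SAP does not say which.

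*The 0/1 cohort is the response and the variable is the factor.* Then F = (X²/(k − 1)) / ((n − X²)/(n − k)), where X² is the chi-square statistic and k the number of levels. Level coding plays no part. Over 2 to 4 levels and cohort shares of 20% to 50%, simulated type I error was 0.042 to 0.053 for both ANOVA and chi-square, with a mean p-value difference below 0.01.

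*The nominal variable is number-coded and used as the response.* Then coding matters. Take a constructed table with 15/7/15 in one cohort (37) and 8/22/8 in the other (38):

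- Chi-square: X² = 12.01 on 2 degrees of freedom, p = 0.0025.
- Cohort as response: F = (12.01/2)/((75 − 12.01)/72) = 6.86, p = 0.0019.
- Variable coded 1, 2, 3 as response: both means are 2.0, F = 0, p = 1.00.
- Codes of levels 2 and 3 swapped: means 1.78 and 2.37, p = 0.0019.

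The table was chosen so that the means tie under one coding. It shows what can happen under that second set-up and does not estimate anything in this trial.

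**The case against.** The strongest reply is that one word is wrong. ANOVA with Pearson is the textbook pair for a continuous outcome, STRA heads the outcome list, and the very next sentence concerns the study outcomes. If cohort was written for outcomes, selection for the STRA models rests on the right association and the harm in step 2 does not arise. This is plausible and may well be what was done, but it is an inference. The SAP does not say so, and on that reading the sentence still states the wrong target. It would also leave the defined cohorts with no stated test, and the three censored outcomes attached to tests that do not suit them.

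A reader might go further and infer that these tests cannot give a valid cohort comparison at all. The documents do not support that. For continuous variables the Pearson test is the t-test. For categorical variables the ordinary meaning of ANOVA makes the variable the factor, and the result then nearly equals chi-square. Dependence on coding needs a number-coded nominal response, which the SAP does not describe.

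It is also fair to say that no stated objective calls for a concurrent versus neoadjuvant comparison. The protocol's objectives and outcome measures contain none, and neither document defines ADT. So the absence of a test for that comparison matters less than the ambiguity over variable selection.

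**Conclusion.** The point holds as a mismatch between test and target that carries into variable selection. The only univariate association described is against the cohort, the regression is for the outcomes, and the named tests suit STRA. This is a wrong statement in the SAP, not merely a missing detail, and it is worth correcting on either reading.

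The size of the harm is conditional. If the cohort screen was used, a predictor with correlation 0.4 to the outcome and no relation to cohort is kept about 5% of the time instead of about 95% (75% to 99.7% for correlations of 0.3 to 0.5). This assumes all 75 cases have data and a 0.05 threshold, which the SAP does not state. If the outcome screen was used, the STRA models are unaffected and only the text is wrong. The documents do not settle which. They do not support calling the cohort comparison invalid.

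**What to change.** Rewrite the univariate and selection sentences of the SAP's Statistical Analysis section along these lines:

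1. Univariate ANOVA (categorical variables) and Pearson correlation (continuous variables) are against STRA only: baseline, 1 year and change. Covariates for the STRA models are selected on association with STRA, at a stated threshold, or on prespecified clinical relevance, and not on association with cohort.
2. Any concurrent versus neoadjuvant comparison uses chi-square or Fisher's exact test for categorical variables and a t-test or Wilcoxon test for continuous ones. Define ADT if this comparison is kept.
3. ANOVA, Pearson correlation and linear regression are not applied to overall, local recurrence-free or distant recurrence-free survival. Name censored-data methods for these, for example Kaplan-Meier estimates and Cox regression.

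The cost is two or three sentences. If selection was in fact done on cohort, the selection step and the STRA models that depend on it must be re-run. If it was done on STRA, the wording alone changes.

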### Data Collection:

Cutaneous toxicity will be assessed at baseline, fraction 15 of XRT and 2 - 5 weeks, 7 - 12 weeks, and 12 – 18 months post XRT by objective ultrasound measurements (UTC). Photographs of the treated breast or chest wall as well as the contralateral breast will also be taken. Documentation of the UTC and photographs will be kept in electronic format for reference. For each visit after the baseline (after treatment has begun), cutaneous toxicity will be assessed by a clinician. Participants will be seen by the investigator in follow up at the third and/or fourth visits and at the fifth visit and an investigator dictation will be performed.

Patients who have had a mastectomy and plan for permanent breast reconstructive surgery after radiation will be assessed within one month of their permanent reconstructive surgery and 5 - 7 months following their surgery using the same procedures as described above. It is highly variable as to when reconstruction will occur. If these time points do not fall within the time frame for the regular study visits, additional study visits will be added for these patients.

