### Secondary Outcome Measures:

- 1. Rate of cutaneous toxicity, as measured by changes in cutaneous measurements, acquired vis ultrasound tissue characterizations (UTC)
- 2. Local control will also be assessed through routine physical examination, annual screening mammograms, ultrasound, and biopsy to confirm local recurrence.
- Blood will be analyzed for biomarkers and inflammatory markers including(tumor necrosis factor (TNF)-alpha, soluble TNF receptor 2 (sTNFR2), interleukin (IL)-6, IL-1ra, and C - reactive protein (CRP) as well as genetic factors to determine if they are associated with development of cutaneous toxicity.
- 4. Change in Multidimensional Fatigue Inventory (MFI) Score

[Time Frame: Baseline, End of Follow Up (Up to 18 months)] [Safety Issue: No]

The Multidimensional Fatigue Inventory (MFI) is a 20-item self-report instrument designed to measure fatigue. Scores range from 20 to 100. The higher the score, the more fatigued.

5. Change in Pittsburgh Sleep Quality Index (PSQI) Score

[Time Frame: Baseline, End of Follow Up (Up to 18 months)] [Safety Issue: No]

The PSQI is a self-rated questionnaire which assesses sleep quality and disturbances over a 1-month time interval. Scores range from 0 to 21. A score of less than or equal to 5 is associated with good sleep quality. A score greater than 5 is associated with poor sleep quality.

6. Change in Perceived Stress Scale (PSS) Score

[Time Frame: Baseline, End of Follow Up (Up to 18 months)] [Safety Issue: No]

The PSS is a self-reported instrument used to measure the perception of stress. Scores range from 0 to 40. Score of 20 or higher are considered high stress.

7. Change in Patient Reported Outcomes Measurement Information System (PROMIS) Fatigue Short Form Score

[Time Frame: Baseline, End of Follow Up (Up to 18 months)] [Safety Issue: No]

The PROMIS Fatigue questionnaire is a self-report tool used to evaluate frequency, duration, and intensity of fatigue over the past seven days. Scores range from 7 to 35. The higher the score, the more fatigue.

8. Change in an Inventory of Depressive Symptomatology-Self Reported (IDS-SR) score

[Time Frame: Baseline, End of Follow Up (Up to 18 months)] [Safety Issue: No]

The IDS-SR is a self-reported measure in which participants rate the frequency of depression symptoms within the past seven days. Scores range from 0 to 84, with higher score reflecting greater severity of depressive symptoms.

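### The SAP names no time-to-event method for its three censored outcomes and does not confine linear regression to skin thickening; LRFS and DRFS are also named as survival endpoints but do not count death

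*SAP*

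**What the plan says.** The SAP section Outcome and definition lists six outcomes. Items 1 to 3 are the skin thickening ratio (STRA) at baseline, at 1 year, and the change between them. Items 4 to 6 are times:

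- "Overall Survival was defined as months from the date of radiation ended to death or last seen at Emory"
- "Local Recurrence-free Survival (LRFS) was defined as months from the date of radiation ended to local recurrence or last seen at Emory"
- "Distant Recurrence-free Survival (DRFS) was defined as months from the date of radiation ended to distant recurrence or last seen at Emory"

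The SAP section Statistical Analysis names descriptive statistics, ANOVA, Pearson correlation and one model: "Multi-linear regression between variables of interest and the study outcomes was examined". On covariates it says: "Variables were selected based on statistical significance on univariate analysis". It cites institutional SAS macros without saying what they do.

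The protocol gives no analysis method for these outcomes. Under Secondary Outcome Measures it describes only how local control is assessed: "Local control will also be assessed through routine physical examination, annual screening mammograms, ultrasound, and biopsy to confirm local recurrence". Under Data Collection it says that local control, distant metastasis and survival are recorded.

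**The concern.** A patient without the event contributes the time to last contact, which is a lower bound on the event time. ANOVA, Pearson correlation and linear regression have no means of separating the two kinds of value. If they are applied to items 4 to 6, the dependent variable is mostly length of follow-up. Two consequences follow. A covariate related to follow-up length can appear related to recurrence or survival, and a real association is more easily missed even when follow-up is balanced. Because covariates enter by univariate significance, an error at that step can pass into the multivariable model.

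The protocol allows last-contact dates to differ between patients. Late assessment is optional ("Patients may also be asked to participate in a long term assessment between 1 and 10 years"), and for those having reconstruction outside the regular visit windows "additional study visits will be added for these patients". Neither passage shows that any covariate is in fact related to follow-up length.

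If the regression was meant for STRA only, the problem is different. Local control, a protocol secondary outcome, then has no stated estimate at any defined time.

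A separate naming point concerns LRFS and DRFS. They are called recurrence-free survival, but death is not among their events. A reader would normally take such a name to mean freedom from both recurrence and death.

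**Working it through.** **Text check.** Right-censored outcomes: 3 of 6. Time-to-event methods named in either document (Kaplan-Meier, log-rank, Cox, cumulative incidence): 0. Statements limiting linear regression to STRA: 0. The plan gives no event count, power or follow-up figure for these outcomes, so there is nothing of its own to reproduce.

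**Simulation of the literal reading.** From the documents:

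- n = 75 (SAP, Data).
- A local recurrence rate of 2.8% at 3 years for the institution's earlier 5-week regimen (Protocol, Background).
- Last contact between 18 and 120 months, taken from the end of the 12–18 month visit and the 10-year limit of the optional assessment.

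Assumed:

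- 3-year event rates of 10% and 20% as alternatives.
- A 30/45 group split.
- Exponential event times T and uniform last-contact times C.
- The size of any follow-up imbalance between groups.

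Linear regression of min(T, C) on group is compared with log-rank on the same data, with 4,000 replicates per scenario.

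| Assumed 3-year event rate | 2.8% | 10% | 20% |
|---|---|---|---|
| Values that are last-contact times (no imbalance) | 95% | 82% | 66% |
| Correlation of months with follow-up length | 0.93 | 0.78 | 0.62 |
| Power at HR 3, no imbalance: linear / log-rank | 9 / 30% | 35 / 72% | 72 / 91% |
| Power at HR 2, no imbalance: linear / log-rank | 6 / 13% | 15 / 33% | 29 / 50% |
| Linear false positives, no imbalance | 5% | 6% | 5% |
| Linear false positives, 3-month imbalance | 7% | 6% | 5% |
| Linear false positives, 6-month imbalance | 13% | 11% | 8% |
| Linear false positives, 12-month imbalance | 36% | 27% | 20% |

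Log-rank false positives were 3–6% throughout.

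**Sensitivity to assumed follow-up.**

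- Last contact uniform over 24–96 months, a 38/37 split and 5-year event risks of 5, 10 and 20%: a 12-month imbalance gives linear false positives of 63, 57 and 45%, against 3–5% for log-rank.
- Last contact over 48–60 months, a 30/45 split and the 3-year rates of the table: power at HR 3 without imbalance is 18, 54 and 79% for linear regression against 25, 67 and 87% for log-rank. A 12-month imbalance gives linear false positives of 75–100%.

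**Expected local recurrences.** 75 × 0.028 = 2.1 by 3 years with full follow-up, and 75 × (1 − 0.947) = 4.0 by last contact in the simulation. For 2 of 75 (2.7%) the exact 95% CI is 0.3–9.3%.

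**Naming point.** Assume 3-year recurrence of 2.8% with deaths censored, and independent constant hazards: 36a = −ln(0.972) for recurrence and 36b = −ln(1 − d) for death without recurrence. Cumulative incidence is a/(a+b) × [1 − exp(−36(a+b))]. Recurrence or death is 1 − 0.972 × (1 − d).

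| Assumed 3-year death, d | 2% | 5% | 10% |
|---|---|---|---|
| As defined (1 − KM, deaths censored) | 2.80% | 2.80% | 2.80% |
| Cumulative incidence of recurrence | 2.77% | 2.73% | 2.66% |
| Recurrence or death | 4.74% | 7.66% | 12.52% |

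The gap is 0.03–0.14 points if recurrence is the target, and about 2 to 10 points if the name is taken at its word.

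**The case against.** The harmful reading may not be what was done. ANOVA, Pearson correlation and linear regression suit the three STRA outcomes. No sentence says that survival months were regressed, the ANOVA and Pearson sentence refers to the study cohort, and the cited macros may include survival routines. With perhaps two to four local recurrences expected, an event count would carry most of the information and no method would support much covariate modelling. The simulated harm depends on assumed follow-up: with no imbalance the false-positive rate is nominal, and with a narrow spread of last-contact dates the loss of power is much smaller. Last contact is not tied to study visits, the 18-month minimum ignores the dropout the protocol expects, and added reconstruction visits need not change the last-contact date. The SAP is written in the past tense, and the outcomes concerned are not primary.

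Most of this stands as a limit on size and scope. The STRA-only reading is plausible, the simulation shows a mechanism and not this trial's bias, and the naming point is a matter of wording if recurrence is the target. None of it supplies the missing method. Under the STRA-only reading, half the listed outcomes still lack a stated analysis beyond descriptive statistics. The unlimited wording would still direct an analyst who follows it to treat last-contact times as event times.

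**Conclusion.** The concern holds. It rests on the text: three censored outcomes, no method for censored times, and a linear model applied to the study outcomes without limit. The SAP needs correction whichever reading was intended. The amount of bias or lost power in this trial cannot be stated, because the event counts, the follow-up distribution and any link between covariates and follow-up are not given. The simulated figures hold only under their stated assumptions.

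The effect is confined to local control, which is a protocol secondary outcome, and to overall survival and DRFS, which are outcomes in the SAP only. The primary toxicity outcomes and the stopping rules are not touched. The mismatch between the LRFS and DRFS names and definitions is a minor point if recurrence is the quantity wanted. It should be fixed, but it does not undermine the trial's main question.

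**What to change.** 1. State that linear regression, and any ANOVA or Pearson analysis of outcomes, applies to the STRA measures only.
2. For overall survival, LRFS and DRFS, define the event, the censoring rule and the event indicator.
3. Report event counts. For overall survival, and for LRFS and DRFS if death is made an event, give Kaplan-Meier estimates with 95% CIs at fixed times, for example 3 years.
4. Make LRFS and DRFS consistent. Either count death from any cause as an event, or rename them local and distant recurrence and report cumulative incidence with death as a competing event. The first choice changes the quantity estimated, so it should be made explicitly.
5. Fit Cox models only if the number of events allows; otherwise state that no covariate model is fitted.

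The cost is SAP wording and standard SAS procedures, since the protocol already collects local control, distant metastasis and survival. The drawback is wide intervals, such as 0.3–9.3% for 2 of 75, and few or no covariate p-values. That reflects how few local recurrences are likely and would be true under any sound method.
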